Antimalarials (chloroquine, hydroxychloroquine, or quinacrine)	≤ 250 mg/day chloroquine (≤ 3 mg/kg/day) ≤ 400 mg/day hydroxychloroquine ≤ 100 mg/day quinacrine	Stable dosing through Week 52. Initiation of new antimalarial treatment is not permitted through Week 52.
Oral glucocorticoids ^b	Stable oral glucocorticoids at minimum prednisone equivalent dose of 10 mg/day and maximum 1 mg/kg/day or ≤ 60 mg/day, whichever is lower.	Week 2 Through Week 12 - tapering starting from Week 2 to prednisone 5 mg equivalent PO daily by Week 12 according to schedule (Appendix 7 [Section 10.7]) Reason(s) for not tapering glucocorticoids should be documented
NSAIDs and other analgesics	Stable dosing through Week 52 with no more than the usual marketed doses approved in the country where the study is being conducted. Notable changes in NSAID dosing to be recorded in concomitant medications. The initiation of treatment with NSAIDs should be avoided unless other analgesics are contraindicated.	
Anti-hypertensive medications (ARBs or ACE inhibitors)	No more than the usual marketed doses approved in the country where the study is being conducted. The initiation of treatment with ARB or ACE inhibitors should be avoided between randomization and Week 52 unless other hypertensive treatments are contraindicated. Substitution of ACE inhibitors for ARBs or ARBs for ACE inhibitors is permitted if medically necessary.	
Non-biologic immunomodulators: MMF MPA	≤ 3 g/day ≤ 2.2 g/day	Stable dosing through Week 52. Initiation of a new immunomodulator is not permitted through Week 52.

^a Permitted concomitant medications are not supplied by the sponsor.

^b Between Weeks 12 and 52, participants requiring average daily doses of glucocorticoids for SLE or LN disease activity that exceed their baseline dose at Week 0 may be categorized as TFs. While these participants will be permitted to remain in the study, the investigator must consider whether glucocorticoid dose increases to an average daily dose ≥ 60 mg prednisone or equivalent for more than 7 consecutive days or whether a requirement for multiple rescues with glucocorticoid therapy between Weeks 12 and 52 should result in discontinuation of study intervention administration (see Section 7.1).

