6.5.5. Non-biologic Immunomodulators

Stable dosing of MMF or MPA as described in [Table 5](#) is required. No other immunomodulators are permitted during the study. A reduction in immunomodulators is allowed only if the participant develops unacceptable side effects, with the implication that this may affect interpretation of the participant’s clinical data. There should be no additions of a new immunomodulator to the existing treatment regimen.

For subjects who initiate MMF (or MPA) during screening or close to screening, the dose should be titrated up during screening based on tolerability to a target dose of ≤ 3.0 grams/day MMF (or equivalent MPA) and kept stable thereafter.

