9.4.2. Primary Endpoint(s)

The primary endpoint is the proportion of participants achieving at least a 50% decrease in proteinuria from baseline at Week 24.

Primary endpoint analysis

Analyses of the primary efficacy endpoint ($\geq 50\%$ decrease in proteinuria from baseline at Week 24) will include data from all randomized participants who received at least one administration of study intervention based on their assigned intervention group, regardless of the actual intervention received and have baseline data (Evaluable population).

Treatment Failure Criteria may include: initiation or increased use of a glucocorticoid or other immunosuppressive agents, however these will be further defined in the SAP.

Participants who meet any of the TF criteria defined in the SAP will be assumed a non-responder, ie, did not meet the $\geq 50\%$ decrease in proteinuria criteria at Week 24.

The primary analysis will be based on the composite estimand where participants meeting TF criteria are assumed non-achievers from the point of TF forward, and missing data are assumed as non-achievers as well.

The study will be considered a success if the 1-sided p-value from the difference in proportion of participants with $\geq 50\%$ decrease in proteinuria between the guselkumab and placebo intervention groups from a logistic MMRM longitudinal model is less than a 1-sided alpha of 10%.

See the SAP for further details about the analysis of the primary endpoint, including sensitivity and subgroup analyses.

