5.3.2.6. Supplementary Estimand 5 (Composite)

a. **Study intervention:**

- Guselkumab (experimental treatment/intervention) in addition to standard-of-care
- Placebo in addition to standard-of-care

b. **Population:** Participants between 18 and 75 with active LN (defined by meeting the classification criteria for SLE by the 2019 European League Against Rheumatism (EULAR)/ACR, having a Class III or IV predominant kidney biopsy documentation of

ISN/RPS proliferative nephritis within the last 6 months prior to or during screening despite receiving one or more standard-of-care treatments.

- c. **Variable:** Responder binary variable, defined as a participant achieving at least 50% decrease in proteinuria from baseline at Week 24 who does not:
- discontinue study intervention for any reason excluding COVID-19 related discontinuations or
 - meet the Medication Intercurrent Event in Section (e) below
- d. **Summary measure (Population-level summary):** Difference in proportion between the study interventions
- e. **Intercurrent events and their corresponding strategies:**

Intercurrent Events	Strategy for Addressing Intercurrent Events and Its Description
Discontinuation (DC) of study intervention for any reason excluding COVID-19 related discontinuations	Composite Strategy: A participant with this intercurrent event is considered to not have achieved at least 50% decrease in proteinuria after this event, the occurrence of this intercurrent event being captured in the variable definition.
Medication Intercurrent Event 
 1. Exceeding baseline glucocorticoid dose 2. Increase above 10 mg/d prednisone equivalent after Week 12, use of new or increased dose of concomitant medication related to LN or other immunosuppressive agents 3. Initiation of prohibited medications at any time prior to the endpoint 
Note: adjustments in glucocorticoids are permitted up to and including Week 12. Nonsystemic glucocorticoids, NSAIDs, antimalarials and topical agents will not be considered an intercurrent event.
	Composite Strategy: Same as above

4. **Difference from Primary Estimand:** The first Medication Intercurrent Event, “Increase above 10 mg/d prednisone equivalent, use of new or increased dose of concomitant medication related to LN or other immunosuppressive agents” can occur at any time after Week 12, not just within 8 weeks prior to the endpoint.

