5.4.2.1.5. Time to Treatment Failure (TF)

Time to TF is defined as time to the first occurrence of TF from baseline. TF is defined as the intercurrent events for the Supplementary Composite Estimand 5 of the primary endpoint in Section 5.3.2.6.

5.4.2.2. Estimand(s)**5.4.2.2.1. Proportion of Participants Achieving Complete Renal Response (CRR) at Week 24****Composite Estimand****1. Study intervention:**

- Guselkumab (experimental treatment/intervention) in addition to standard-of-care
- Placebo in addition to standard-of-care

2. Population: Participants between 18 and 75 with active LN (defined by meeting the classification criteria for SLE by the 2019 European League Against Rheumatism (EULAR)/ACR, having a Class III-IV kidney biopsy documentation of ISN/RPS proliferative nephritis within the last 6 months prior to or during screening despite receiving one or more standard-of-care treatments.

3. Variable: Responder binary variable, defined as a participant achieving Complete Renal Response (CRR) at Week 24 who does not:

- discontinue study intervention for any reason excluding COVID-19 related discontinuations or
- meet the Medication Intercurrent Event in Section (5) below

4. Summary measure (Population-level summary): Difference in proportion between the study interventions

5. Intercurrent events and their corresponding strategies:

Intercurrent Events	Strategy for Addressing Intercurrent Events and Its Description
Discontinuation (DC) of study intervention for any reason excluding COVID-19 related discontinuations	Composite Strategy: A participant with this intercurrent event is considered to not have achieved CRR after this event, the occurrence of this intercurrent event being captured in the variable definition.
Medication Intercurrent Event 
 1. Exceeding baseline glucocorticoid dose 2. Increase above 10 mg/d prednisone equivalent after Week 12, use of new or increased dose of concomitant medication related to LN or other immunosuppressive agents, within 8 weeks prior to the endpoint 3. Initiation of prohibited medications at any time prior to the endpoint 
Note: adjustments in glucocorticoids are permitted up to and including Week 12. Nonsystemic glucocorticoids, NSAIDs, antimalarials and topical agents will not be considered an intercurrent event.
	Composite Strategy: Same as above

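### SAP 5.3.2.6 contradicts itself on whether an MMF/MPA increase before Week 12 is a treatment failure, and the 8-week window lets a treatment failure dated before Week 16 count as a Week 24 responder

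*SAP*

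**What the plan says.** **Treatment failure.** SAP 5.4.2.1.5 states that "TF is defined as the intercurrent events for the Supplementary Composite Estimand 5 of the primary endpoint". In that estimand (SAP 5.3.2.6), medication item 2 reads "Increase above 10 mg/d prednisone equivalent after Week 12, use of new or increased dose of concomitant medication related to LN or other immunosuppressive agents". The note in the same cell reads "Note: adjustments in glucocorticoids are permitted up to and including Week 12". The paragraph headed Difference from Primary Estimand restates item 2 without its inner Week 12 phrase and then says the event "can occur at any time after Week 12, not just within 8 weeks prior to the endpoint".

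**Reported responder estimands.** In SAP 5.3.2.1 (primary), item 2 carries an added limit of 8 weeks before the endpoint. The main estimands for CRR and both UPCR thresholds at Week 24, for proteinuria and CRR at Week 52, and for time to CRR use the same wording. Item 3 covers starting a prohibited drug. Stopping study drug for any non-COVID reason is a separate event.

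**Protocol.** The MMF/MPA row of Table 6 (section 6.5) reads "Stable dosing through Week 52. Initiation of a new immunomodulator is not permitted through Week 52". Section 6.5.5 allows reductions only, for side effects, and for participants who begin MMF/MPA at or near screening "the dose should be titrated up during screening based on tolerability to a target dose". Section 9.4.2 says TF criteria may include "initiation or increased use of a glucocorticoid or other immunosuppressive agents", leaves the detail to the SAP, and makes anyone meeting the SAP's criteria a non-achiever from that point on. SAP Appendix 2, on changes to protocol-planned analyses, reads N/A.

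**The concern.** MMF/MPA is the background therapy to which guselkumab or placebo is added, and it acts on the same proteinuria endpoint. The steroid taper runs from Week 2 to Week 12, so pressure to raise the background dose is likely to be greatest then. If guselkumab works, that pressure should be greater on placebo.

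Two things are at stake. First, two programmers following SAP 5.3.2.6 could date TF differently for the same participant, which changes the time-to-TF analysis. Second, a participant can be a TF in one reported analysis and a responder in another, although the protocol makes TF imply non-response. If such participants are more common on placebo, counting their responses pulls the two response rates together.

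Other rules close part of the gap. A newly started immunosuppressant is caught as a prohibited drug. A change made for an LN flare requires stopping study drug (Protocol 6.5), which is itself an intercurrent event. An MMF/MPA increase made without a declared flare, or titration that runs on after randomisation, is caught by neither.

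**Working it through.** **Step 1: the texts side by side.** Take an MMF/MPA increase above the randomisation dose, with study drug continued, dated by the day of the increase. The look-back for Week 24 opens at 24 - 8 = Week 16, and for Week 52 at 52 - 8 = Week 44.

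| Week of increase | TF by the 5.3.2.6 table and note | TF by the 5.3.2.6 Difference sentence | Non-responder at Week 24 by 5.3.2.1 |
|---|---|---|---|
| 6 | yes | no | no |
| 14 | yes | yes | no |
| 18 | yes | yes | yes |

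The Week 6 row is the contradiction within 5.3.2.6. The Week 14 row does not depend on it: under either reading the participant is a TF, yet remains eligible as a primary responder.

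The part of the 24 weeks in which an increase escapes item 2 is:
- 5.3.2.6 table: 0 weeks
- Difference sentence: Weeks 0-12, 12/24 = 50%
- 5.3.2.1 window: Weeks 0-16, 16/24 = 67%

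**Step 2: the plan's own power figure.** Inputs from SAP section 3: placebo 49%, difference 30 points (guselkumab 79%), total 60 (30 per arm), one-sided alpha 0.10. Exact binomial enumeration of the pooled two-proportion z test gives 89.84%, matching the SAP. It also gives the stated 79.61% at 25 points and 96.08% at 35 points. The 20-point row does not reproduce (65.87% against a stated 56.34%), but nothing here uses it.

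**Step 3: an illustration of size.** The documents give no rate of MMF/MPA increase, so these inputs are assumptions:
- a = proportion on placebo with an early increase: 5%, 10%, 15%
- b = proportion on guselkumab: 0%, 3%, 5%
- r = proportion of those who then meet the endpoint: 40%, 60%, 80%
- 49% and 79% are taken as the rates when all such participants are scored as failures

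If their responses count instead, placebo rate = 0.49 + a x r and guselkumab rate = 0.79 + b x r. Power is from the Step 2 method at 30 per arm.

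| a, b, r | Placebo | Guselkumab | Difference | Power |
|---|---|---|---|---|
| 15%, 0%, 80% | 0.49 + 0.12 = 0.61 | 0.79 | 18 points | 61% |
| 10%, 3%, 60% | 0.49 + 0.06 = 0.55 | 0.79 + 0.018 = 0.808 | 25.8 points | 83% |
| 5%, 5%, 80% | 0.49 + 0.04 = 0.53 | 0.79 + 0.04 = 0.83 | 30 points | 91% |

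The first and last rows are the extremes of the 27 combinations: 18 to 30 points and 61% to 91%. With a = b = 10%, both rates rise by 4 to 8 points and the difference stays at 30.

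**The case against.** **The operative text is the table, not the comparison sentence.** TF is defined by the intercurrent events, which the table lists. There the Week 12 phrase sits on the prednisone limb, and the note limits the allowance to glucocorticoids. Read literally, a Week 6 MMF increase is a TF. The comparison sentence is loose in other ways too: it calls item 2 the first event. This stands, and it is why the point is an inconsistency. A reader might infer that the SAP plainly extends the steroid grace period to immunosuppressants, so that an early increase is never a TF. The documents do not support that: the table and note say otherwise, and flare-driven increases lead to stopping study drug, which counts as TF.

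**The quoted sentence does not turn such responses into successes.** Of the reported analyses, Estimand 5 feeds only time to TF, which has no response component. SAP 5.3 drops its responder analysis from the CSR. This also stands. The effect on the primary endpoint comes from the 8-week window, and the weeks concerned are 0-16.

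**The window is a deliberate estimand choice and the protocol is permissive.** Protocol 6.5 and 9.4.2 say non-compliant adjustments and increased immunosuppressants *may* be TF, and Table 6 governs conduct. This stands in part. The SAP was free to define TF narrowly. Having defined it, Protocol 9.4.2 makes those participants non-responders from TF forward, and the window departs from that without being declared.

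**Continued use might count.** Item 2 refers to use of an increased dose, so someone still on a raised dose in Weeks 16-24 could be caught. That reading is possible, but nothing in the SAP settles it.

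**Conclusion.** The point holds as two linked defects. SAP 5.3.2.6 gives two answers for an immunosuppressant increase in Weeks 0-12, and the TF definition inherits both. Independently, the 8-week window in the primary and secondary main estimands allows a TF dated before Week 16 to be a Week 24 responder, which conflicts with Protocol 9.4.2 and is not declared in Appendix 2. Neither defect depends on assumed rates.

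The numerical effect is not known. The 18-30 points and 61%-91% power rest on assumed increase and response rates, on treating 49% and 79% as the rates under strict scoring, and on 30 per arm, which the terminated study will not reach. A reader might infer that the primary comparison is certainly diluted. That follows only if early increases are more common on placebo. No effect on time to TF has been quantified. The matter merits correction because it is cheap and affects reported endpoints.

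**What to change.** Before the single database lock:

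1. Split item 2 in SAP 5.3.2.6 so that the Week 12 phrase attaches only to the glucocorticoid limb.
2. Correct the Difference sentence so that, for TF, a new or increased immunosuppressant, including MMF/MPA above the randomisation dose, counts at any time after randomisation. Say whether the event is dated by the increase or by continued use.
3. Reconcile the 8-week window in 5.3.2.1 and the secondary main estimands with Protocol 9.4.2. Either score participants with a TF-defining immunosuppressant increase as non-responders from that date, or list the departure in Appendix 2 and report the primary endpoint under Estimand 5 as a sensitivity analysis.

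This concerns analysis classification only and sets no dosing rule. The cost is SAP wording and, under the second option, one more analysis. Protocol 6.5 already has concomitant therapies and their dosing recorded in the eCRF. The downside is a few more non-responders, including some whose titration simply ran late.

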5.3.3. Analysis Methods

Unless otherwise specified, the population for analysis will be the FAS defined in Section 4 for the primary and its respective sensitivity analyses.

Simple descriptive statistics, such as n, mean, standard deviation (SD), median, interquartile (IQ) range, minimum and maximum for continuous variables and counts and percentages for discrete variables will be used to summarize most data.

For the primary analysis, the primary composite estimand will be targeted.

Generalized linear model with logit link for a binary mixed effects repeated measures model (MMRM) will be used to analyze the data. The model will include all available observed data after applying intercurrent events with treatment, visit, region, baseline UPCR level (<3 mg/mg and ≥ 3 mg/mg), and treatment and visit interaction in the model will be used to analyze the data. The 1-sided p-value from the difference in proportion of participants with $\geq 50\%$ decrease in proteinuria from baseline at Week 24 between the intervention groups will be provided. In addition, the estimate and its 80% confidence interval (CI) estimated from the model will also be provided.

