9. STATISTICAL CONSIDERATIONS

Due to the sponsor's decision to terminate the study early, some analyses described below may not be performed. The primary efficacy analysis and most secondary efficacy analyses will be performed. All safety analyses will be performed.

For informational purposes, the below section outlines the original statistical plan.

Statistical analysis will be done by the sponsor or under the authority of the sponsor. A general description of the statistical methods to be used to analyze the efficacy and safety data is outlined below.

Specific details will be provided in the revised SAP.

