9.4. Statistical Analyses

The SAP will include a more technical and detailed description of the statistical analyses described in this section. This section is a summary of the planned statistical analyses of the more important endpoints including primary and key secondary endpoints.

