9.4.3. Secondary Endpoint(s)

Major secondary endpoints include:

1. Proportion of participants achieving CRR at Week 24.
2. Proportion of participants achieving a sustained reduction in steroid dose ≤ 10 mg/day of prednisone or equivalent from Week 16 to Week 24.

3. Proportion of participants achieving at least 50% decrease in proteinuria from baseline at Week 52.
4. Proportion of participants achieving CRR at Week 52.
5. Proportion of participants with UPCR <0.5 mg/mg at Week 24.
6. Proportion of participants with UPCR <0.75 mg/mg at Week 24.
7. Time to CRR.
8. Time to TF.

Secondary endpoint analyses

The Evaluable population will be used for analysis and participants will be counted in the intervention group assigned, regardless of the study intervention received.

Treatment failure and missing data will be included in the secondary endpoint estimands as non-achievers or non-responders.

The details of the analysis of the major secondary endpoints will be included in the SAP.

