5.3.1. Definition of Endpoint(s)

The primary endpoint is the proportion of participants achieving at least 50% decrease in proteinuria from baseline at Week 24. Proteinuria is based on UPCR.

Variable specific data handling rules: Observed data will be used for the analysis.

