5.3.5. Sensitivity Analyses

5.3.5.1. Sensitivity Analysis 1 (Primary Composite Estimand)

“Tipping Point” via exhaustive scenarios will be used. A two-dimensional tipping point analysis of exhaustive scenarios for all missing data at Week 24 will be performed on the primary endpoint to evaluate the missing at random assumption for the Composite Estimand. For participants with missing proteinuria data at Week 24, the data will be imputed in an increasing manner by participant for each treatment intervention. Specifically, imputation starts where all participants do not achieve 50% decrease in proteinuria up to the scenario where all participants achieved 50% decrease in proteinuria. This would include all possible scenarios including scenarios where participants on guselkumab have worse outcomes than participants on placebo. The analysis method for the primary analysis in Section 5.3.3 will be used.

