5.4.2.3.1. Binary Endpoints (Secondary Endpoints 1-6)

Analyses for binary secondary endpoints (proportion of response, improvement, reduction) will be based upon the estimands in Section 5.4.2.2.1 through Section 5.4.2.2.6.

Generalized linear model with logit link for a binary MMRM will be used to analyze the data for Secondary Endpoints 1 and 3-6 (main and supplementary). The model will include all available observed data after applying intercurrent events with treatment, visit, region, baseline UPCR level (<3 mg/mg and ≥ 3 mg/mg), and treatment and visit interaction in the model will be used to analyze the data. The 1-sided p-value from the difference in proportion of participants between the intervention groups will be provided. In addition, the estimate and its 80% CI estimated from the model will also be provided.

Logistic regression model will be used to analyze Secondary Endpoint 2 (main and supplementary). The model will include treatment, region, and baseline UPCR level (<3 mg/mg and ≥ 3 mg/mg). The 1-sided p-value, the odds ratio and the corresponding 80% CI between the intervention groups from the model will be provided.

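### The protocol counts missing outcomes as non-response; the SAP analyses observed data, declares no change, and drops the only missing-data check on the reported primary estimand

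*SAP*

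**What the plan says.** **Protocol.** Section 9.4.2 describes a composite estimand in which participants meeting treatment-failure criteria are "non-achievers from the point of TF forward, and missing data are assumed as non-achievers as well". Section 9.4.3 carries the rule to the major secondary endpoints: "Treatment failure and missing data will be included in the secondary endpoint estimands as non-achievers or non-responders". The synopsis repeats both. The early-termination text at the head of Section 9 says of what follows: "For informational purposes, the below section outlines the original statistical plan". It also states that the primary analysis and most secondary analyses will still be performed, with details in the revised SAP.

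**SAP.** Section 5.3.1 gives the data rule for the primary endpoint: "Observed data will be used for the analysis". Section 5.3.3 fits a binary repeated-measures model and states: "The model will include all available observed data after applying intercurrent events". Section 5.4.2.3.1 uses the same model and data rule for secondary endpoints 1 and 3-6. In the primary estimand (5.3.2.1), only two kinds of event become non-response: discontinuation for reasons other than COVID-19, and the listed medication events.

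Section 5.3.5.1 plans a tipping-point analysis "to evaluate the missing at random assumption for the Composite Estimand". The opening note to 5.3 limits the CSR to the primary composite estimand analysed by the 5.3.3 method, which removes that analysis. The note to 5.4 keeps only the main estimand of each secondary endpoint. Appendix 2, the place for changes to protocol-planned analyses, reads N/A.

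**The concern.** These are two different rules for deriving the same outcome. A participant still on treatment whose Week 24 UPCR is missing is a non-responder under the protocol. Under the SAP that participant contributes no Week 24 value.

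A revised SAP may change the rule, but the change should be recorded, and Appendix 2 says there is none. The SAP version history does not mention it either. The tipping-point analysis would have shown whether the choice matters. Its first scenario sets every missing Week 24 value to non-response, which at that visit is the protocol's rule. Dropping it therefore also drops the nearest thing to the protocol-specified result.

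With fewer than 60 participants, a few such values can move the 1-sided p-value across 0.10, the success criterion in protocol 9.4.2 and in the SAP's original sample-size section.

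**Working it through.** **1. Is the difference real?** The SAP phrase about applying intercurrent events could be read as covering all missing data. The table in 5.3.2.1 does not support that reading: a missed visit or an unusable sample is neither a discontinuation nor a medication event. Section 5.3.5.1 settles it, because it names missing at random as the assumption for the composite estimand and imputes missing Week 24 values. Under the protocol's rule none would remain.

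**2. Which values are affected?** Missed visits, unusable samples, and COVID-19 discontinuations with no later data. Footnote c of the protocol's main-study Schedule of Activities allows follow-up after discontinuation, and SAP 5.3.2.5 implies that the primary estimand uses it. Termination itself should add little: participants on treatment have a final efficacy visit about 4 weeks after the last dose, and Week 52 endpoints use FASC52.

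**3. Is there another check on this estimand?** No. The multiple imputation (5.3.4.2) serves the hypothetical estimand and the second tipping point (5.3.5.2) the treatment-policy estimand. No missing-data analysis is planned for the secondary endpoints.

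**4. Size.** Inputs from the SAP sample-size section: 49% on placebo, a 30-point difference (so 79%), 1-sided alpha 0.10, total 60. The test used is the pooled z-test, with responders a of n on placebo and b of m on guselkumab:

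z = (b/m − a/n) / √[p̄(1 − p̄)(1/n + 1/m)], where p̄ = (a + b)/(n + m).

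*Plan's own figure.* Exact enumeration of two binomials at 30 per arm gives 89.84% power, equal to the stated value. The 25- and 35-point rows (79.61%, 96.08%) also reproduce. The 20-point row does not (65.87% against the stated 56.34%); that is a separate matter and is not used here.

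*One constructed data set, 30 per arm.* Placebo has 14 responders among 28 observed (2 missing); guselkumab has 18 among 26 observed (4 missing).

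- Observed data: difference 0.692 − 0.500 = 0.192; p̄ = 32/54 = 0.593; SE = 0.134; z = 1.44; p = 0.075.
- Missing as non-response: difference 18/30 − 14/30 = 0.133; p̄ = 32/60 = 0.533; SE = 0.129; z = 1.04; p = 0.150.

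The first meets the criterion and the second does not.

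*How often this happens.* Of 2n Week 24 values, k are missing at random, split between arms by the hypergeometric distribution. Responders are binomial at 79% and 49%. Arm sizes are assumptions within the stated limit of fewer than 60.

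| n per arm | k | Opposite calls | Pass on observed data only | Pass under non-response only |
|---|---|---|---|---|
| 12 | 1 | 10.8% | 8.0% | 2.8% |
| 12 | 2 | 19.2% | 14.9% | 4.4% |
| 12 | 3 | 16.4% | 13.5% | 2.9% |
| 18 | 1 | 9.0% | 3.7% | 5.3% |
| 18 | 2 | 6.9% | 4.5% | 2.4% |
| 18 | 3 | 13.3% | 6.8% | 6.5% |
| 25 | 1 | 5.2% | 4.1% | 1.1% |
| 25 | 2 | 5.8% | 4.1% | 1.7% |
| 25 | 3 | 7.9% | 6.3% | 1.6% |
| 28 | 1 | 5.2% | 2.6% | 2.7% |
| 28 | 2 | 3.6% | 2.4% | 1.2% |
| 28 | 3 | 7.2% | 4.4% | 2.8% |

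Flips go both ways. At 18 per arm with three missing, the overall chance of p < 0.10 barely changes (70.2% observed, 69.9% non-response). At 12 and 25 per arm it is about 2 to 11 points lower under non-response.

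A random-intercept logistic simulation at 18 per arm gave 9.8%, 13.8% and 16.3% for one, two and three missing. It assumed a random-intercept SD of 2 and a weak penalty, and omitted region; the SAP specifies no covariance structure for this model.

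**The case against.** **The SAP governs and is consistent.** Protocol Section 9 is labelled the original plan, and 9.4 defers to the SAP: "The SAP will include a more technical and detailed description of the statistical analyses described in this section". The SAP applies one rule throughout, so on this view the defect is one missing Appendix 2 entry. Most of this stands: the SAP probably does govern. But the protocol keeps the primary analysis in force, the outcome's derivation has changed, and Appendix 2 denies any change.

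**The residual is small.** Most dropouts already become non-response through the intercurrent-event rules, and no passage gives a rate for the rest. This stands as a limit on size. Such gaps are foreseeable, though: the protocol's COVID-19 and regional-disruption guidance expects missed visits, and SAP Appendix 4 lists them as deviations.

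**The illustration overstates importance.** The flip rates do not rise steadily with the number missing, which partly reflects the discreteness of a simple test that is not the planned model, and they are lower at 28 per arm. That is correct, and the figures should be read only as showing that the two calls can differ.

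**The CSR is abbreviated and the cuts are declared.** True, and nothing is concealed. Counts by visit might also let a reader rebuild crude non-response proportions. They would not show whether the reported p-value and 80% CI depend on the rule. A secondary-endpoint table would be a new request and is optional.

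**The tipping point imputes Week 24 only**, whereas the protocol's rule names no visit. True, so the two coincide at the endpoint visit but not necessarily across every visit in the model.

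**Conclusion.** The concern holds. The protocol and SAP give different missing-data rules for the primary endpoint and secondary endpoints 1 and 3-6. Appendix 2 records no change, and the CSR will contain no planned test of missing data under the reported composite estimand. Secondary endpoint 2 is outside the point because it uses a separate logistic regression.

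Confidence is high on the text. The effect on results cannot be known from the documents and is nil if nothing is missing without an intercurrent event. Under the assumptions above, one to three missing Week 24 values give opposite calls in 3.6% to 19.2% of trials across 12 to 28 per arm, in either direction. No one-way bias is claimed. It should be corrected before database lock.

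**What to change.** Before unblinding:

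1. State in the SAP which missing-data rule governs the primary endpoint and secondary endpoints 1 and 3-6.
2. If it is the observed-data model, list it in Appendix 2 as a departure from protocol 9.4.2 and 9.4.3.
3. Keep the tipping-point analysis of SAP 5.3.5.1 in the CSR for the primary endpoint. It is already specified and includes the case where every missing Week 24 value is non-response.
4. Optionally, add one table for secondary endpoints 1 and 3-6 with missing counted as non-response.

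The cost is a sentence or two of SAP text, one Appendix 2 entry and one or two tables. No new data are needed. The estimate under non-response may be higher or lower than the observed-data estimate.
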